14.1.3. Allocation of Adverse Events to Analysis Periods

All adverse events records will be placed into analysis periods considering their start date(time), i.e. aiming to report the incidence of these events only in the analysis period during which they started.

The general rule for allocation of AEs to analysis periods follows:

Analysis period start date(time) \leq AE start date(time) \leq analysis period end date(time)

If the start date(time) of an AE is incomplete and to such a level preventing a clear allocation of the AE to one single analysis period, a worst-case consideration will be done aiming to allocate the AE record to one single analysis period, if possible. The CRF question “Did the adverse event start prior to the first dose of study treatment?” will also be considered for the analysis period allocation.

When a worst-case consideration is needed for allocation to analysis periods, the end date of the AE records, if and as available, should also be considered; if such AEs clearly end on a given point, this will exclude the possibility to allocate the AE to an analysis period after that point.

- An AE which according to the available information of its start date(time) could belong to the screening and to the treatment analysis period will only be placed in the treatment analysis period.
- An AE which according to the available information of its start date(time) could belong to the treatment analysis period and to the Follow-up analysis period will only be placed in the treatment analysis period.

14.1.4. Treatment Relatedness

Following (ICH-E3), the originally reported relatedness to study drug of an AE will be dichotomized as follows:

- Not study drug related: this includes the levels ‘unrelated’, ‘unlikely’ and ‘not applicable’.
- Study drug related: this includes the levels ‘possible’, ‘probable’ and ‘certain’ (includes, as a worst-case consideration, any missing drug relatedness).

This dichotomized relatedness will only be used in tables; relatedness as originally reported will only be listed.

14.1.5. Worst-case Selections

When cross-tabulating AE preferred terms versus an AE attribute (e.g., intensity), the worst-case is always applied within each subject, preferred term and analysis period, i.e., when a subject has multiple times the same AE preferred term in the same analysis period, then the subject is reported only once: only with the worst intensity. If this happens in two different analysis periods, the AE is reported twice: once in each analysis period.

CRF will collect the changes in AE. If there is a change of intensity, seriousness, drug relatedness or action taken, the worst category (by analysis period when applicable) will be considered for tables.

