5. DEFINITION OF ANALYSIS PERIODS, OF ANALYSIS TIME POINTS, AND OF BASELINE

5.1. ANALYSIS PERIODS FOR NON-VISIT DATA

These analysis periods are to be used for allocation of events into periods (e.g., adverse events).

Analyses Periods for Non-Visit Data

| Analysis period | Start period | End Period |
|---|--|---|
| Screening | Date of signing the ICF, with 00:00 added as time part. | 1 minute before the date/time of first dose of study medication* |
| Treatment | First dose of study medication date/time* | Last dose of study medication date + 30 days, with 23:59 added as time part.# |
| Follow-up | Last dose of study medication date + 31 days, with 00:00 added as time part# | Study discontinuation date, with 23:59 added as time part. |
| * For endpoints without time collected, all assessments done on the day of the first dose will be assigned to the treatment period. | | |
| # Time midnight is used as switch point to conservatively assign endpoints to the treatment period if on the date of last dose of study medication + 30 days. | | |

Note that the last analysis period in case of early discontinuation will always be ended by the study discontinuation date (date of last contact in the study).

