14.1.7. Calculation of Percentages

The denominator for all percentages will be the total number of subjects in each treatment group within the analysis period.

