14.1.8. Tables

Analysis periods will be replaced by their respective treatment via the randomization list (i.e., an as-randomized allocation) in all tables and listings.

Table 14.3.1.1: Treatment-emergent adverse events: Summary table

Tabulation per treatment group of the incidence of subjects:

- With at least one treatment-emergent adverse event (TEAE);
- With at least one serious TEAE;
- With at least one ISR;
- With at least one skin related TEAE;
- With at least one ISR (Grade 3 or higher) or skin related TEAE;
- With at least one AE leading to death;
- With at least one mild TEAE as worst intensity per treatment;
- With at least one moderate TEAE as worst intensity per treatment;
- With at least one severe TEAE as worst intensity per treatment;
- With at least one life threatening TEAE as worst intensity per treatment;
- With at least one fatal TEAE as worst intensity per treatment;
- With at least one TEAE considered related to study drug;
- With at least one TEAE for which the study drug was temporarily stopped;
- With at least one TEAE for which the study drug was permanently stopped.

Population: safety analysis set.

Table 14.3.1.2: Treatment-emergent adverse events up to 30 days after last dose: Summary table

Same as [Table 14.3.1.1](#), but restricted to events that started after start of study medication and up to 30 days after last dose.

Population: safety analysis set.

Table 14.3.1.3: Treatment-emergent adverse events: Tabulation of all adverse events

Incidence of subjects tabulation per treatment group of TEAE classified per system organ class and preferred term.

Population: safety analysis set.

Table 14.3.1.4: Treatment-emergent adverse events up to 30 days after last dose: Tabulation of all adverse events

Same as [Table 14.3.1.3](#), but restricted to events that started after start of study medication and up to 30 days after last dose.

Population: safety analysis set.

Table 14.3.1.5: Treatment-emergent adverse events: Tabulation of all adverse events by preferred term

Incidence of subjects tabulation per treatment group of TEAE classified per preferred term.

Population: safety analysis set.

Table 14.3.1.6: Treatment-emergent adverse events up to 30 days after last dose: Tabulation of all adverse events by preferred term

Same as [Table 14.3.1.5](#), but restricted to events that started after start of study medication and up to 30 days after last dose.

Population: safety analysis set.

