Table 14.3.1.7: Treatment-emergent adverse events: Tabulation of all adverse events – Alphabetic order

Same as [Table 14.3.1.3](#) but sorted by alphabetic order.

Population: safety analysis set.

Table 14.3.1.8: Treatment-emergent adverse events up to 30 days after last dose: Tabulation of all adverse events – Alphabetic order

Same as [Table 14.3.1.3](#), but restricted to events that started after start of study medication and up to 30 days after last dose and sorted by alphabetic order.

Population: safety analysis set.

Table 14.3.1.9: Treatment-emergent adverse events: Tabulation per worst intensity

Cross-tabulation of incidence of subjects per treatment group of TEAE preferred terms classified per system organ class versus their intensity. Considering the worst-case intensity per TEAE preferred term and per subject in each treatment group.

Population: safety analysis set.

Table 14.3.1.10: Treatment-emergent adverse events: Tabulation of all treatment-related events

Same as [Table 14.3.1.3](#), but restricted to the AEs categorized as related to study drug.

Population: safety analysis set.

Table 14.3.1.11: Treatment-emergent adverse events: Tabulation of treatment-related events per worst intensity

Same as [Table 14.3.1.9](#), but restricted to the AEs categorized as related to study drug.

Population: safety analysis set.

Table 14.3.1.12: Treatment-emergent adverse events: Tabulation of all injection site reaction events

Same as [Table 14.3.1.3](#), but restricted to the ISR events.

Population: safety analysis set.

Table 14.3.1.13: Treatment-emergent adverse events: Tabulation of all injection site reaction events per worst intensity

Same as [Table 14.3.1.9](#), but restricted to the ISR events.

Population: safety analysis set.

Table 14.3.1.14: Treatment-emergent adverse events: Tabulation of all skin related events

Same as [Table 14.3.1.3](#), but restricted to the skin related events.

Population: safety analysis set.

Table 14.3.1.15: Treatment-emergent adverse events: Tabulation of all skin related events per worst intensity

Same as [Table 14.3.1.9](#), but restricted to the skin related events.

Population: safety analysis set.

Table 14.3.1.16: Treatment-emergent adverse events: Tabulation of all events for which the study or study treatment were discontinued

Same as [Table 14.3.1.3](#), but restricted to the TEAEs for which the study treatment was permanently discontinued, or for which the study was discontinued.

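### SAP 14.1.5 selects worst adverse event intensity per analysis period and reports a repeated term twice; the severity tables select it once per subject, and the SAP does not say which rule governs

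*SAP*

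**What the plan says.** **Periods.** SAP 5.1 splits the time after first dose in two. The end of Treatment is "Last dose of study medication date + 30 days, with 23:59 added as time part"; the start of Follow-up is "Last dose of study medication date + 31 days, with 00:00 added as time part". SAP 14.1.2 treats every event from first dose to last contact as treatment-emergent, so TEAEs fall in both periods.

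**General counting rule.** SAP 14.1.5 deals with cross-tabulating preferred terms against an attribute such as intensity. It says "the worst-case is always applied within each subject, preferred term and analysis period". For a term that occurs in both periods it adds: "If this happens in two different analysis periods, the AE is reported twice: once in each analysis period". A later sentence, on recorded changes within an event, is softer: "the worst category (by analysis period when applicable) will be considered for tables".

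**Table rules.** SAP 14.1.8 opens with "Analysis periods will be replaced by their respective treatment via the randomization list (i.e., an as-randomized allocation) in all tables and listings". Table 14.3.1.9 then has its own instruction: "Considering the worst-case intensity per TEAE preferred term and per subject in each treatment group". Tables 14.3.1.11 (related events), 14.3.1.13 (injection site reactions) and 14.3.1.15 (skin events) are defined by reference to it. The summary Table 14.3.1.1 classifies subjects by worst intensity per treatment.

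**Denominator.** SAP 14.1.7 says "The denominator for all percentages will be the total number of subjects in each treatment group within the analysis period". SAP 7.6 sets the default as the subjects in a treatment group.

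**The concern.** The two counting rules give different tables from the same data. Selecting once per period and then labelling both periods with the same randomized arm leaves two records for one subject and one preferred term in one column. That would do no harm in a crossover, where periods map to different treatments. In this parallel-group trial both post-dose periods map to the same arm.

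Severity of TEAEs is part of the primary endpoint (SAP 2.3.1), and Tables 14.3.1.9, 14.3.1.11, 14.3.1.13 and 14.3.1.15 report it by preferred term. If 14.1.5 were followed in these tables, the intensity rows for a term could add up to more than its incidence in Table 14.3.1.3, with the surplus in the lower grades. Two programmers could produce different tables, each citing the SAP.

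**Working it through.** The plan gives no figure for this point. Its only design figure, the 87% in protocol 7.1, reproduces as 1 − 0.95^40 = 0.871 and plays no part here.

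**1. Can one term fall in both periods?** Dosing is on Days 1, 15, 29 and 43 (protocol 4.1). With a last dose on Day 43:
- Treatment ends on Day 43 + 30 = Day 73.
- Follow-up runs from Day 43 + 31 = Day 74 to Day 169, which is 169 − 74 + 1 = 96 days.

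So recurrence across the boundary is possible for any subject who stays in the study. Recurrence may not even be needed. SAP 14.1.2.1 treats a post-dose worsening as a new event, and SAP 14.1.3 allocates records by start date. On that reading, one event that is mild on Day 60 and worsens on Day 80 gives a record in each period.

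**2. The two rules on the same data.** Take three subjects in one arm with the same preferred term (invented data):

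| Subject | Treatment | Follow-up |
|---|---|---|
| 1 | Grade 1 | Grade 3 |
| 2 | Grade 2 | none |
| 3 | none | Grade 1 |

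| Rule | Grade 1 | Grade 2 | Grade 3 | Entries | Subjects |
|---|---|---|---|---|---|
| SAP 14.1.5, both periods pooled into the arm | 2 | 1 | 1 | 4 | 3 |
| Table 14.3.1.9 | 1 | 1 | 1 | 3 | 3 |

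The extra entry is subject 1 at Grade 1. The Grade 3 count is the same under both rules. If the two periods had the same worst grade, the row would be inflated only if records rather than distinct subjects were counted.

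**3. Size per affected subject.** With the planned arm sizes (protocol 7.1), one extra entry adds 1/40 = 2.5 percentage points to the row total on MOR106 and 1/20 = 5 points on placebo. The documents do not say how many subjects would be affected. For an assumed 1 to 4 per arm the excess is:
- MOR106: 1/40 to 4/40, or 2.5 to 10 points.
- Placebo: 1/20 to 4/20, or 5 to 20 points.

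Under the Table 14.3.1.9 rule the excess is 0.

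**4. The 30-day tables.** Tables 14.3.1.2, 14.3.1.4, 14.3.1.6 and 14.3.1.8 stop at 30 days after last dose, which is the Treatment period of SAP 5.1. Only one period is present, so the two rules agree there.

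**The case against.** **The tables define themselves.** A definition attached to a table normally governs that table. Table 14.3.1.9 and the three tables that inherit from it place each subject in one row per preferred term, and Table 14.3.1.1 follows the same principle. This stands. A reader might infer that the primary severity tables will count subject-periods rather than subjects, but the documents do not support that.

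**The replacement sentence may be the remedy.** The opening of SAP 14.1.8 can mean that treatment takes the place of period as the grouping unit. The worst case would then be per subject, term and treatment, which is once per subject here. The SAP's list of defined terms ties an analysis period to exposure to a single study drug or combination, which fits. But the sentence can equally mean that both periods receive the same arm label and both records stay. SAP 5.1 also departs from the defined term by dividing one arm's post-dose time in two. The ambiguity remains.

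**The denominator.** A reader might also infer from SAP 14.1.7 that percentages rest on a wrong base, because a subject who leaves within 30 days of the last dose has no Follow-up period. That does not follow. Every adverse event table is per treatment group on the safety analysis set, every subject in that set has a Treatment period, and no follow-up-only adverse event table is planned. With the default in SAP 7.6, no planned percentage changes.

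**Limited harm.** Even under 14.1.5 each subject's highest grade is shown, so no severe event is hidden. Incidence in Table 14.3.1.3 does not use the intensity rule, and the adverse event tables are descriptive. The 96 days of Follow-up show that recurrence is possible, not how often it occurs. All this stands and limits the size of the point.

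The layouts are in a separate mock-up document (SAP 7.9.3) that was not available, and it may already settle the matter.

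**Conclusion.** SAP 14.1.5 contradicts the definitions of the severity tables it is meant to serve. It says its rule always applies, the table definitions say otherwise, and the SAP sets no order of precedence. If 14.1.5 is followed, a subject with different worst grades in the two periods enters two intensity rows of the same arm: 2.5 points per subject on MOR106 and 5 on placebo, at 40 and 20 subjects. If the table rule is followed, the excess is nil. The table rule is probably what the sponsor intends.

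The finding is therefore a conflict of rules that puts the severity part of the primary endpoint at risk, not a certain double count. It rests on the absence of period columns in the adverse event tables as described in SAP 14.1.8. The number of affected subjects is unknown; the range of 1 to 4 is only illustrative.

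**What to change.** In SAP 14.1.5, state that the worst case is taken once per subject and preferred term over all TEAEs included in the given table. That means the whole TEAE window in general, and events up to 30 days after last dose for the restricted tables. Delete the sentence on reporting a term twice.

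Keep the period allocation in SAP 14.1.3. Tables 14.3.1.2, 14.3.1.4, 14.3.1.6 and 14.3.1.8 need it to place events with incomplete dates, and listings such as 16.2.10.2 are shown by period.

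Optionally, align SAP 14.1.7 with SAP 7.6 by giving the denominator as the safety analysis set subjects in each arm. This only tidies the wording.

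The cost is one sentence changed and one deleted, plus a check that the table mock-ups agree. No new data are needed, and the primary endpoint does not change.

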14.1.6. Adverse Event Onset Day and Duration

See section [Calculation of Relative Days and Durations](#).

For each AE record, its onset day in study (the day of the AE start date relative to the date of administration of study drug), its onset day in the analysis period, and its duration in days will be calculated and shown only in listings.

These relative onset days, and the AE duration will be set to missing if the AE start date is incomplete or missing.

If the AE end date is incomplete, the AE duration will be set to missing.

If the AE end date is missing, the AE duration will be calculated until the date of last contact in the study for the concerned subject, printing such AE duration as '>X days'.

If the outcome of an AE is 'not resolved' or equivalent, the AE duration will be calculated with either the provided AE end date or until the date of last contact in the study for the concerned subject (whichever is earliest/available), also printing such duration as '>X days'.

Since worsenings of intensity, seriousness, drug relatedness or action taken are recorded in the CRF, two durations will be computed:

- The duration (days) of the individual event: the duration of the event until worsening or until resolution or until the date of last contact (whatever applies).
- The duration (days) of the overall event: the duration of the event until the end of the worsening or until resolution or until the date of last contact (whatever applies).

If there is no worsening, the individual event duration and the overall event duration will be equal. In case of worsening, for the event(s) stating for the worsening(s), only the individual event duration will be computed. For the initial event, both durations will be computed as for the events without worsening.

14.1.7. Calculation of Percentages

The denominator for all percentages will be the total number of subjects in each treatment group within the analysis period.

14.1.8. Tables

Analysis periods will be replaced by their respective treatment via the randomization list (i.e., an as-randomized allocation) in all tables and listings.

Table 14.3.1.1: Treatment-emergent adverse events: Summary table

Tabulation per treatment group of the incidence of subjects:

- With at least one treatment-emergent adverse event (TEAE);
- With at least one serious TEAE;
- With at least one ISR;
- With at least one skin related TEAE;
- With at least one ISR (Grade 3 or higher) or skin related TEAE;
- With at least one AE leading to death;
- With at least one mild TEAE as worst intensity per treatment;
- With at least one moderate TEAE as worst intensity per treatment;
- With at least one severe TEAE as worst intensity per treatment;
- With at least one life threatening TEAE as worst intensity per treatment;
- With at least one fatal TEAE as worst intensity per treatment;
- With at least one TEAE considered related to study drug;
- With at least one TEAE for which the study drug was temporarily stopped;
- With at least one TEAE for which the study drug was permanently stopped.

Population: safety analysis set.

Table 14.3.1.2: Treatment-emergent adverse events up to 30 days after last dose: Summary table

Same as [Table 14.3.1.1](#), but restricted to events that started after start of study medication and up to 30 days after last dose.

Population: safety analysis set.

Table 14.3.1.3: Treatment-emergent adverse events: Tabulation of all adverse events

Incidence of subjects tabulation per treatment group of TEAE classified per system organ class and preferred term.

Population: safety analysis set.

Table 14.3.1.4: Treatment-emergent adverse events up to 30 days after last dose: Tabulation of all adverse events

Same as [Table 14.3.1.3](#), but restricted to events that started after start of study medication and up to 30 days after last dose.

Population: safety analysis set.

Table 14.3.1.5: Treatment-emergent adverse events: Tabulation of all adverse events by preferred term

Incidence of subjects tabulation per treatment group of TEAE classified per preferred term.

Population: safety analysis set.

Table 14.3.1.6: Treatment-emergent adverse events up to 30 days after last dose: Tabulation of all adverse events by preferred term

Same as [Table 14.3.1.5](#), but restricted to events that started after start of study medication and up to 30 days after last dose.

Population: safety analysis set.

Table 14.3.1.7: Treatment-emergent adverse events: Tabulation of all adverse events – Alphabetic order

Same as [Table 14.3.1.3](#) but sorted by alphabetic order.

Population: safety analysis set.

Table 14.3.1.8: Treatment-emergent adverse events up to 30 days after last dose: Tabulation of all adverse events – Alphabetic order

Same as [Table 14.3.1.3](#), but restricted to events that started after start of study medication and up to 30 days after last dose and sorted by alphabetic order.

Population: safety analysis set.

Table 14.3.1.9: Treatment-emergent adverse events: Tabulation per worst intensity

Cross-tabulation of incidence of subjects per treatment group of TEAE preferred terms classified per system organ class versus their intensity. Considering the worst-case intensity per TEAE preferred term and per subject in each treatment group.

Population: safety analysis set.

Table 14.3.1.10: Treatment-emergent adverse events: Tabulation of all treatment-related events

Same as [Table 14.3.1.3](#), but restricted to the AEs categorized as related to study drug.

Population: safety analysis set.

Table 14.3.1.11: Treatment-emergent adverse events: Tabulation of treatment-related events per worst intensity

Same as [Table 14.3.1.9](#), but restricted to the AEs categorized as related to study drug.

Population: safety analysis set.

Table 14.3.1.12: Treatment-emergent adverse events: Tabulation of all injection site reaction events

Same as [Table 14.3.1.3](#), but restricted to the ISR events.

Population: safety analysis set.

Table 14.3.1.13: Treatment-emergent adverse events: Tabulation of all injection site reaction events per worst intensity

Same as [Table 14.3.1.9](#), but restricted to the ISR events.

Population: safety analysis set.

Table 14.3.1.14: Treatment-emergent adverse events: Tabulation of all skin related events

Same as [Table 14.3.1.3](#), but restricted to the skin related events.

Population: safety analysis set.

Table 14.3.1.15: Treatment-emergent adverse events: Tabulation of all skin related events per worst intensity

Same as [Table 14.3.1.9](#), but restricted to the skin related events.

Population: safety analysis set.

Table 14.3.1.16: Treatment-emergent adverse events: Tabulation of all events for which the study or study treatment were discontinued

Same as [Table 14.3.1.3](#), but restricted to the TEAEs for which the study treatment was permanently discontinued, or for which the study was discontinued.

Population: safety analysis set.

Table 14.3.1.17: Serious treatment-emergent adverse events: Tabulation for EudraCT reporting

Frequency tabulation per treatment group of serious TEAEs per system organ class and preferred term, showing both the number of subjects and events themselves.

Population: safety analysis set.

Table 14.3.1.18: Non-serious treatment-emergent adverse events: Tabulation for EudraCT reporting

Same as [Table 14.3.1.17](#), but restricted to the non-serious TEAEs.

Population: safety analysis set.

Table 14.3.1.19: Non-serious treatment-emergent adverse events: Tabulation for EudraCT reporting of TEAEs occurring in at least 5% of the overall subjects

Same as [Table 14.3.1.17](#), but restricted to the non-serious TEAEs.

All the lines from the table where there is at least 5% occurrence (of the subjects) of the overall subjects either at system organ class or at preferred term level will be displayed. If the system organ class line is selected but none of the associated preferred terms, then the system organ class will still be presented but without preferred terms.

Population: safety analysis set.

